As the incidence of joint disease continues to increase, an ever growing percentage of the affected population may choose to have total knee arthroplasty (TKA).^{1, 2, 3, 4} This recent upward trend appears to be directly related to the prevalence of certain health factors. Specifically, longer life spans, rising obesity rates, and increasing physical activity levels in relatively younger populations are all examples of health factors that may significantly contribute to knee degeneration.^{3, 5, 6} While strategies such as weight reduction, lifestyle change or drug therapy may offer temporary relief from the symptoms of knee degeneration, TKA remains the standard of care for subjects experiencing significant losses in quality of life due to advanced osteoarthritic disease.^{1, 3}

Contemporary advances in TKA are allowing for improved surgical techniques and implant designs. Given such a positive track record, surgeons have relatively high expectations for device safety and function. Moreover, both surgeons and subjects alike are placing increasing emphasis on the recovery of function postoperatively.^{8, 9, 10, 11} Therefore, once a device is introduced into a market, research focusing on clinical outcomes is essential in order to assess whether or not surgeon and subject expectations are being met. In addition, this data can be used to support the design rationale of future devices.

Factors affecting clinical outcomes following TKA include subject age, subject activity level, preoperative range-of-motion, gender, anatomic variation, preoperative joint pathology and metal sensitivity. Clinically successful devices must be versatile in order to address variation between cases.

I. STUDY OBJECTIVES

The objective of the current study is to establish the safety and efficacy of the LEGION® Primary Total Knee System at each postoperative time point using the following parameters:

A. Efficacy Criteria

- The Knee Society Clinical Rating System¹⁵ (KSS) will provide separate measures of knee pain and subject function. The primary efficacy outcome measure will be passive flexion. Range of motion for the KSS score will be determined using a goniometer.
- The Knee Osteoarthritis Outcomes Score (KOOS) will be used as a self-administered measure of subject health status. Specifically, the KOOS score will allow for the assessment of pain, stiffness, and overall physical function.
- Serial radiographic follow-up of study subjects by the Clinical Investigator using the Knee Society Roentgenographic Evaluation and Scoring System.¹⁶ The purpose of the radiograph evaluation at short-term follow-up is to assess baseline knee alignment. At mid-term follow-up and long-term follow-up, the focus of the

radiographic evaluations are to assess any evidence of loosening as indicated primarily by radiolucencies $\geq 2\text{mm}$; lack of evidence of surface wear or particulate debris generation as indicated by early osteolysis, implant migration, or other clinical or radiographic abnormalities. A flexed lateral radiograph will be taken and used to obtain the flexion angle.

B. Safety Criteria

- Surgical and knee-related adverse events, including revision, will be reported during the conduct of this study.
- The frequency of revisions and knee related adverse events.

C. Health Economic Criteria

- Intraoperative data, including operative time, blood loss and surgical related complications will be assessed.

II. DEVICE DESCRIPTION AND PROCEDURES

The LEGION[®] Total Knee System is a comprehensive system designed to allow surgeons to address straightforward primary to complex knee arthroplasty. The LEGION[®] Total Knee System consists of oxidized zirconium or cobalt-chrome primary femoral components, titanium primary tibial components, and a polyethylene patella. In addition, conventional and cross linked polyethylene tibial inserts are available in both traditional and high flexion options. The resulting product is sufficient to accommodate a wide range of clinical applications.

Various instruments are required that allow the surgeon to assemble the components and prepare the bones to accept the implants. These instruments are routinely utilized as part of the standard LEGION[®] Total Knee System surgical procedure. Instruments of the device system are typically manufactured from stainless steel meeting applicable American Society for Testing and Materials (ASTM) standards. Handles of some instruments are made of plastic or aluminum. Additionally, various general surgical instruments and bone shaping tools such as chisels, saws, knives, curets, drills, etc. may be used that are a generic component of any orthopaedic operative procedure.

III. RISKS

There are risks associated with any knee replacement procedure that may result from the surgery itself, the device that is implanted, or the instrumentation used to implant the device. This study does not involve investigational products as all components have been cleared for use by the FDA and are commercially available. Product labeling is available to outline product risks for this device. The risk of this surgery should be explained to the subject as part of the consent for surgery.

Study assessment includes radiographic evaluation. Risks may be associated with radiographic evaluation as part of the routine care involving TKA procedures and exposure to more radiation due to the increased number of x-rays the subject will undergo in follow-up. X-ray exposure risk is cumulative over a lifetime, and total exposure should be kept as low as possible. Additional risks associated with this study include the loss of confidentiality and the risks associated with blood collection. Blood collection procedures require that a sterile needle be placed into a vein. This may be associated with some discomfort as the needle is inserted into the vein. Other complications may occur such as blood or fluid leaking or collecting under the skin and forming a bruise, mild irritation of the skin or tissue in the area, and infection at the blood draw site.

The risks associated with this study include:

- Loss of confidentiality
- Exposure to additional radiation due to the increased number of x-rays patient will undergo during follow-up visits.

X-ray exposure risk is cumulative over a lifetime, and the total should be kept as low as possible.

IV. STUDY DESIGN

This is a prospective, consecutive series, multi-center clinical study of the LEGION® Total Knee System. The study design was selected to assess the safety and effectiveness profile of the LEGION® Total Knee System in subjects with degenerative knee disease requiring primary total knee replacement.

Subjects meeting the entrance criteria specified in this protocol will be approached to participate in the study and enrolled sequentially. Any consenting subjects meeting the inclusion criteria are not to be excluded unless they do not consent to participate. A nonrandomized, consecutive series of up to 138 subjects will be enrolled at a maximum of 8 research sites, with an expectation of 18 subjects (up to a maximum of 28 subjects) to be enrolled at each site. When 138 subjects are enrolled from all sites, enrollment will be stopped, regardless of the number contributed from each site. Sites will be selected for participation in the study at the discretion of Smith & Nephew.

Follow-up clinical assessments will be at Operative/Discharge, 3 months, 1 year, 2 years, 3 years, 5 years, 7 years and 10 years. Each subject will receive a standard radiographic evaluation at discharge that will be used for baseline analysis. Additional radiographic analysis will be performed at Operative/Discharge, 3 months, 1 year, 2 years, 3 years, 5 years, 7 years and 10 years.

The primary endpoint will be:

- Cumulative percent survival

The secondary endpoints will be:

- Surgical and device related adverse events
- Knee Society Score (KSS)
- Knee Osteoarthritis Outcome Score (KOOS)
- Radiographic evaluation

V. STUDY POPULATION

A. Subject Selection Criteria

The subject population considered for this study is osteoarthritic subjects requiring a total knee replacement. The following inclusion and exclusion criteria will be used to identify study candidates. It is very important that every subject who meets these entry criteria be enrolled into the study and that no subjects be disregarded or omitted for other reasons. A method should be established upon beginning the study whereby all potential study candidates are given the opportunity to participate sequentially.

B. Inclusion Criteria

Subjects must meet all of the inclusion criteria:

1. Subject is a candidate for the LEGION® Primary Knee System according to the instructions for use;
2. Subject is of legal age and skeletally mature;
3. Subject is willing to sign and date an ethics-approved consent form and participate in the study;
4. Subject is willing to be available for ten-year follow-up postoperatively.

C. Exclusion Criteria

Subjects must not meet any of the exclusion criteria:

1. Subject with immunosuppressive disorders;
2. Subject has grossly insufficient femoral or tibial bone stock;
3. Subject has an active localized or systemic infection;
4. Subject is pregnant;
5. Subject psychological or neurological conditions that would impair the subject's ability or willingness to restrict activities or follow medical advice during the course of this study;
6. Subject is a prisoner.

VI. STUDY PROCEDURES

A. Prior to Study Initiation

The following documents must be provided to Smith & Nephew prior to study initiation:

1. Copies of the IRB approval letter and IRB approved informed consent for each institution used by the Investigator for the clinical study.
2. A signed Statement of Investigator.
3. A current, signed, dated CV and medical license for the Principal Investigator documenting the location where the study will be conducted.

B. Subject Enrollment

1. Screen Subject – All subjects who present with total knee osteoarthritis requiring joint replacement will be screened for eligibility in the study based on physical exam and radiographic evaluation of the joint.
2. Informed Consent – If the subject meets all inclusion and exclusion criteria, a consent form is presented to the subject. If the subject elects to participate in the study, the subject must sign the consent form prior to completing any study related activities.
3. Preoperative Evaluation – After the subject meets the entrance criteria and signs the consent form, the appropriate preoperative study activities are to be completed.

C. Operative Procedures

1. Surgical Technique

The medical device will be implanted using standard surgical technique(s), depending on the individual investigator's standard procedure. Instrumentation specific for the device will be used. A surgical technique brochure for implanting the LEGION® Total Knee System will be provided to each investigator.

2. Operative Data

Operative data and device information will be collected. All operative adverse events will also be reported.

D. Postoperative Procedures

Adverse events occurring during the hospital stay will be reported. Discharge information will also be captured.

E. Follow-up Procedures

Subjects will be evaluated clinically at 3 months, 1 year, 2 years, 3 years, 5 years, 7 years, and 10 years postoperative. Please see Section I, "Schedule of Events" Table for details and visit windows.

All radiographic observations are to be reported on the radiographic form. Postoperative device-related and surgical adverse events are to be reported.

All reasonable efforts should be made to keep in contact with the subject for the 10 year duration of this study.

F. Radiographic Procedures

The important aspects of successful joint arthroplasty are component position, joint alignment, and the prosthesis-bone interface or fixation.

In order to assess the safety and efficacy of the current study device, radiographic evaluations will be performed during regular follow-up intervals up to the ten year postoperative visit.

It is absolutely critical that positioning errors be minimized so that accurate and consistent measurements can be taken for all device components. Radiographs are to be taken and reported Operative/Discharge, 3 months, 1 year, 2 years, 3 years, 5 years, 7 years, and 10 years postoperatively. The span of the bone-prosthesis interface obtained in these 3 views (AP/lateral/skyline) for each component is broken down into zone systems. The scoring system for each of the three components is determined by measuring the radiolucent lines (in millimeters) for each of these zones.

Any other radiograph views taken are at the discretion of the individual clinician.

G. Adverse Events

The following are definitions of adverse events:

Adverse event - any undesirable clinical occurrence in a subject, regardless of the cause

Device-related adverse event - an adverse event that is related to device use, e.g. component breakage

Unanticipated adverse device effect (UADE) - an event that is not identified in nature, severity, or frequency in the current package label or informed consent

Serious/severe adverse event - an event that is

- 1) Life threatening or fatal,
- 2) Requires or prolongs hospitalization,
- 3) Results in permanent impairment of a body function, or
- 4) Results in permanent damage to a body structure.

All postoperative device-related and surgery-related adverse events are to be reported. Specifically, all component removals (and/or revisions) whether device-related or not must be recorded. Other adverse events not listed here may be classified as device-related (or non-device-related) depending on their frequency, medical significance, and circumstance. Device-related adverse events (complications) are defined as any of the following:

- Any device implant component failure (e.g. breakage)
- Device-wear particle-induced osteolysis, inflammation, etc. Wear debris may be metal, cement, and/or HA in composition.
- Any device component experiencing dislocation, subluxation, subsidence, or migration.

All serious adverse events, life-threatening problems, or deaths that occur during or following the use of the devices during the study should be fully documented in the research record by the Investigator including the onset date, complete description of the event, severity, duration, action taken, and outcome. The event should be documented on the appropriate interval and case report form. The investigator will be responsible for notifying the reviewing ethics committee or IRB of any unanticipated adverse events. The Investigator will record all non-serious, device-related adverse events on the appropriate case report form. All adverse events must be followed until they resolve, or are considered final.

Adverse events that are serious, unanticipated and possibly device-related must be reported in detail by the Investigator to Smith & Nephew and the reviewing IRB as soon as possible, but in no event later than ten working days after the Investigator first learns of the event.

H. End of Study

Study completion status of the subject (e.g. completed per protocol, subject withdrawal, device removed, death, lost-to-follow-up, or other reason) is to be recorded. A subject having a specified objection to continuing in the study will be withdrawn. Any subject who withdraws from the study postoperatively will be considered in the data analysis up until the time of their withdrawal. Subjects lost to follow-up will be documented on the End of Study form. All reasonable efforts should be made to keep in contact with the subject for the 10 year duration of this study.

Subjects may be taken out of the study without their consent for the following reasons:

- ✓ The Investigator decides that continuing the study would be harmful
- ✓ Participants miss so many appointments that their data cannot be used in the study
- ✓ The study Sponsor (Smith & Nephew, Inc.) decides to end the study

If a subject is unwilling to return to the site for evaluation, available information may be collected on the subject's condition via telephone or correspondence. Participation in this study is completely voluntary. If any subject chooses not to participate or removes their consent at any time, subject care must continue according to the physician's standard of care. The site must document changes in subject enrollment via a de-identified summary and forward this information to the sponsor. All subjects who complete the study prematurely will be included in the data analysis up until the time of their study completion.

I. Schedule of Events

Study Activity	Preop	O/D	3 mo (± 2 mo)	1 yr (± 3 mo)	2 yr (± 6 mo)	3 yr (± 1 yr)	5 yr (± 1 yr)	7 yr (± 1 yr)	10 yr (± 1 yr)
Inclusion/exclusion Form	X	-	-	-	-	-	-	-	-
Informed Consent	X	-	-	-	-	-	-	-	-
Demographics/ Med History Form	X	-	-	-	-	-	-	-	-
Clinical KSS/KOOS	X	-	X	X	X	X	X	X	X
Operative/Discharge Form	-	X	-	-	-	-	-	-	-
Radiograph Analysis	-	X	X	X	X	X	X	X	X
Adverse Event Form	-	†	†	†	†	†	†	†	†
End of Study/Exit Form	-	-	†	†	†	†	†	†	†

† This form should be completed when necessary.

VII. DATA COLLECTION

A. Case Report Forms

Case report forms (CRF) will be used to collect the data obtained during this study. Data must be transcribed from source documentation to CRFs. Subject questionnaire data will be recorded directly onto the provided CRFs, and will not be transferred from source documentation.

The CRFs are a set of forms that include questions to record preoperative, operative, discharge, postoperative and x-ray information. A complete set of CRFs will be provided for each subject enrolled.

Smith & Nephew, Inc. currently uses the DataFax data collection system. It allows for case report forms to be faxed directly into the database system. Using this system will increase the speed and efficiency of data collection from the study sites, and will improve the quality of the study data through the use of automated missing data queries. DataFax will also track subject visits according to the scheduled intervals. Periodic due/overdue reports will be sent to the clinical site to help ensure subjects are evaluated at the appropriate intervals.

Investigators are required to fax all completed CRFs to Smith & Nephew at **[contact]**, at the appropriate intervals to ensure consistent, accurate analysis of study data. Any parameters not collected may adversely impact the quality and validity of the final results of this study. Special care should be taken to record any device-related or surgical adverse event including a complete description of their relationship to the study device.

Source Documents – Investigators are responsible for obtaining and maintaining complete subject health information in the medical record for each subject and each assessment (source documents).

Source data includes all information in original records and certified copies of original records of clinic findings, observations or other activities in a clinical trial necessary for the reconstruction and evaluation of the trial. Source data are contained in source documents (e.g., hospital records, clinic evaluation, transcriptions, operative notes, x-rays, radiology reports, blood collection and shipment records, research subject files, etc.)

Every data point that is found on the CRF and submitted to the Sponsor must have a corresponding source document in the subject record(s) that provides detailed evidence of the assessment. The Sponsor and its agents will be provided direct access to source documents for the purpose of verifying the clinical data submitted to the Sponsor by the investigator on CRFs.

B. Data Quality Assurance

Quality assurance procedures are designed to ensure that complete, accurate and timely data are submitted, that protocol requirements are followed, and that complications or adverse reactions are immediately identified and addressed until closure.

The Clinical Affairs Department at Smith & Nephew, Inc. will promptly review all incoming case report forms and accompanying documentation to identify inconsistent or missing data and device-related complications. Problems with these data will result in queries to the site that should be addressed within two weeks of receipt. *It is incumbent upon the site to review all data recorded on each form prior to submission to Smith & Nephew, Inc.* To ensure the confidentiality of data, Smith & Nephew, Inc. will maintain a secure study database.

Protocol Deviation – Protocol deviation is defined as any non-adherence to the protocol or Investigational Plan. Protocol deviations will be reported to Smith & Nephew on the appropriate Case Report Form. The investigator must also report protocol deviations to the IRB as required.

Modification of the Protocol – Neither the Investigator nor Sponsor will modify this protocol without mutual agreement. After agreement to initiate the modification (in the form of a protocol amendment), the Investigator agrees not to institute this modification until instructed to do so by the Sponsor. It may be necessary to obtain applicable regulatory authority and IRB/EC approval prior to implementation of any change in the protocol that may affect the scientific soundness or the rights, safety, or welfare of the subjects involved.

Departure from Protocol for Individual Subject in Emergency – Only in an emergency where action is necessary to protect the life or physical well-being of the subject will a departure from the protocol for an individual subject be allowed, and the departure will be for that subject only. The investigator or other physician in attendance in such circumstances will notify the IRB and contact the clinical study manager at Smith & Nephew immediately (within 48 hours) by telephone. If the study manager is unavailable, contact the next available Smith & Nephew Clinical Affairs professional.

[name], CCRA
[contact]
Email: [contact]
Smith & Nephew, Inc.
[name]
[name]

A decision will be made by the investigator and Smith & Nephew about whether the subject (for whom the departure from protocol was affected) is to continue in the study. Any departure from the protocol will be described in a written report by the investigator who will send the report to the IRB and Smith & Nephew along with the reasons for the departure, including relationship to the therapeutic use of the device.

VIII. STATISTICAL METHODS

A. Literature Control

For the current investigation, a historical control has been determined using the Australian Orthopedic Association National Joint Replacement Registry Annual Report 2009 (See below).

Survival Estimate of Primary Knee Replacement (Annual revision free rate * follow-up interval in years)

	1 year	3 year	5 year	7 year	8 year
F Total Knee	99.0%	97.2%	96.2%	95.4%	95.0%

For the current study, the revision free rate will be based on knowledge of parametric proportional hazards models. The survival times with an exponential distribution have a constant hazard function associated with exponential distributed survival time. Thus, for individuals sampled from this exponential survival distribution, the probability of surviving beyond time $t=8$ years is 0.95. The entire survival distribution can be defined by the same parameter value $\lambda=0.0064$ (nQuery Advisor 6.01).

B. Non-inferiority Analysis

As previously reported, an annual survival rate was extrapolated using equivalency of exponentially distributed survival times to determine 10 year survivorship. As such, the current 10-year investigation will utilize a control survival rate of approximately 93.7% (nQuery Advisor 6.01).

All subjects implanted with the LEGION® Primary Knee System, who meet the inclusion and exclusion criteria and who gave their voluntary consent to participate in the study will be included in the analysis. The analysis will include the description of subject demographics and baseline characteristics. Accountability data will include the number of subjects enrolled and the followup data collected. Data will be analyzed separately for changes from preoperative at 3 months, 1 year, 2 years, 3 years, 5 years, 7 years, and 10 years(if required). Safety will be assessed by identifying and summarizing device-related adverse events throughout the study.

The sample size is calculated based on the non-inferiority of the study device; the following hypotheses will be tested to test the difference in cumulative percent survival of the study device with the literature reference rate with a non-inferiority margin, $\delta>0$:

$$H_0: \pi_0 - \pi \geq \delta$$

$$H_a: \pi_0 - \pi < \delta$$

Where π is the cumulative percent survival of study device and π_0 is the reference rate, respectively. $\delta=0.07$. For these hypotheses, rejection of the null hypotheses will imply non-inferiority of the study device compared to the reference rate.

For the above hypotheses, the sample size for a specified α and power $100(1 - \beta)\%$ is given by,

$$n = \frac{(z_\alpha + z_\beta)^2 [\pi (1 - \pi)]}{(\pi_0 - \pi - \delta)^2}$$

(Chow et al, 2003), where δ is the non-inferiority margin and nonnegative number.

The cumulative percent survival for the study device is unknown for this population, but there is no reason to believe that it would be less than the reference rate. Therefore, a conservative success rate of 93.1% for the study device is used at 10 years. The non-inferiority margin δ of 0.07 is chosen in the study (p13, Chow, Shao, and Wang, 2003). 96 subjects are required to achieve $100(1 - \beta)\% = 80\%$ power to detect non-inferiority at the Significance level of $\alpha = 0.05$. Based on the experience study, allowing 30% of the subjects lost to follow up by the end of 10 years, a sample size of at least 138 subjects are needed in this study. Therefore, a total of 138 subjects will be enrolled into the study in up to 8 clinical sites.

C. Statistical Methods

Primary and secondary outcomes will be evaluated with the use of listings and summary statistics. 95% confidence intervals will be calculated for proportions and averages corresponding to the clinically significant outcomes. Improvement in pain and function will be analyzed using t-test or Wilcoxon Rank tests. Kaplan-Meier estimates will be used to analyze the survivorship of the prosthesis. For survivorship analyses, revision will be defined as failure. Adjustment of prognostic factors to the improvement in outcomes will be performed if needed using appropriate parametric or non-parametric statistical analysis. All statistical analyses and calculation of confidence intervals will be performed using SAS or other appropriate statistical software. An alpha value of $\alpha=0.05$ will be used in all hypothesis testing.

Experience from numerous studies has revealed that most of the missing data are usually due to lost to follow-up, revision, death and subject withdrawal. A complete accountability along with the explanation for lost-to-follow-up, death, revision, and withdrawn subjects will be provided in the final study report. The missing due to revision will be treated as device failure. A complete assessment of the informative/non-informative missing data will be performed using Kaplan-Meier (KM) method. The KM estimate of the success rate along with the 95% confidence interval of the estimate will be included in the final report.

IX. STUDY SUPERVISION

A. Investigator Responsibilities

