7.10 Analysis of Primary Endpoint

- Kaplan-Meier product limit survival estimates will be used to estimate implant (device) survivorship, $S(t)$ where $S(t)$ is the proportion of knees without an implant revision at time t . Time to implant revision is the endpoint of interest in the determination of implant survivorship. The cumulative proportion of knees with implant survivorship at 3 months, 12 months (1 year), 24 months (2 years), 36 months (3 years), 60 months (5 years), 84 months (7 years) and 120 months (10 years) will be estimated and displayed accordingly. Knees that are still on-study without a revision will be censored on that date of database lock. A prematurely discontinued knee from study as a result of death or for any other reason will be censored on the discontinuation date. A subject lost to follow-up prior to the database lock will have the contributory knee censored on the last known contact date. Kaplan-Meier estimates for implant survivorship will be presented with the corresponding two-sided 95% Confidence Intervals (CIs). Kaplan-Meier survival graphs will also be displayed.
- A listing of subjects with revised implants and the components revised would be provided.
- The Kaplan-Meier product limit estimates will further be presented after stratifying by age group, BMI group and gender.

CONFIDENTIAL AND PROPRIETARY

This document contains information that is confidential and proprietary to Smith & Nephew PLC and Smith & Nephew, Inc. and is intended for use only by Smith+Nephew and its manufacturer. It shall not be reproduced or copied in whole or in part, nor shall the contents be disclosed by any means without prior written permission from Smith+Nephew, nor shall anyone make any use of it that is contrary to the expressed or implied wishes of Smith+Nephew.

Statistical Analysis Plan

A Prospective, Multi-Center, Non-Randomized, Safety and Efficacy Clinical Study of the LEGION™ Primary Knee System for Primary Total Knee Replacement in Subjects with Degenerative Knee Disease

Number: 10-4042
ST: 1113
Version: Final 1.0, 15-Feb-2021
Page: 16 of 18

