7.15 Changes in Analysis Methods Specified in the Protocol

The protocol-specified analysis of the primary endpoint was planned to be inferentially performed using a non-inferiority approach. This study is now being terminated early, thus, the primary endpoint will only be descriptively summarized.

CONFIDENTIAL AND PROPRIETARY

This document contains information that is confidential and proprietary to Smith & Nephew PLC and Smith & Nephew, Inc. and is intended for use only by Smith+Nephew and its manufacturer. It shall not be reproduced or copied in whole or in part, nor shall the contents be disclosed by any means without prior written permission from Smith+Nephew, nor shall anyone make any use of it that is contrary to the expressed or implied wishes of Smith+Nephew.

Smith+Nephew

Statistical Analysis Plan

A Prospective, Multi-Center, Non-Randomized, Safety and Efficacy Clinical Study of the LEGION™ Primary Knee System for Primary Total Knee Replacement in Subjects with Degenerative Knee Disease

Number: 10-4042
ST: 1113
Version: Final 1.0, 15-Feb-2021
Page: 18 of 18

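### The protocol promises that Kaplan-Meier will assess informative missing data, which it cannot do, and the SAP neither plans a survivorship sensitivity analysis nor records the gap

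*Protocol*

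**What the plan says.** Protocol VIII.C defines revision as failure, says that data missing because of revision count as device failure, promises an accounting of losses, deaths, revisions and withdrawals, and then adds: "A complete assessment of the informative/non-informative missing data will be performed using Kaplan-Meier (KM) method". No other method is named for this purpose.

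The SAP turns this into censoring rules. Under 7.10, "A prematurely discontinued knee from study as a result of death or for any other reason will be censored on the discontinuation date", and "A subject lost to follow-up prior to the database lock will have the contributory knee censored on the last known contact date". Unrevised knees still on study are censored at database lock. The only further survivorship estimates are strata by age, BMI and gender. SAP 7.3 deals with missing data only for Knee Society Score (KSS) items. SAP 7.15, the section for departures from the protocol, records one change: "This study is now being terminated early, thus, the primary endpoint will only be descriptively summarized".

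Several provisions limit or display the loss:
- Protocol VI.H: "Any subject who withdraws from the study postoperatively will be considered in the data analysis up until the time of their withdrawal". It also lists removal of the device among the exit statuses and, for subjects unwilling to return, says that "available information may be collected on the subject's condition via telephone or correspondence".
- Protocol VI.G: "all component removals (and/or revisions) whether device-related or not must be recorded".
- Protocol XI.B and XI.D provide for tracing of subjects who cannot be located. XI.D requires a final evaluation and a documented reason for every subject who does not finish, but rules out further follow-up after withdrawal.
- SAP 7.6 provides a disposition table by visit.

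**The concern.** A KM estimate uses a knee's history only up to its censoring time. Whatever happens to that knee later, the estimate is the same, so KM cannot distinguish informative from non-informative loss. The protocol therefore names a method that cannot deliver the stated assessment, and the SAP supplies no other analysis that could.

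With the non-inferiority test withdrawn, the KM estimate and its confidence interval (CI) are the whole primary result. The CI measures sampling error under the assumption of non-informative censoring. If knees that leave are revised at a different rate from knees that stay, the estimate is off by an amount the CI does not show, and a reader of the protocol could believe the question had been examined.

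**Working it through.** **Plan figures.** The allowance for loss is 30% by 10 years: 96/(1 - 0.30) = 137.1, rounded up to the stated 138. The stated hazard also reproduces: -ln(0.95)/8 = 0.0064 per year. Neither document gives observed loss, revisions or numbers at risk, so what follows is an illustration.

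**KM does not respond to informative loss.** Take a constant hazard with 10-year survival of 93.1% (the protocol's assumption), 30% loss spread over the ten years, and a revision hazard after loss of r times that of retained knees. In simulation (n = 138, 4,000 runs) mean KM stays at about 93.1% for r = 1, 3, 5 and 10. True survival is 93.1%, 91.1%, 89.3% and 85.4%.

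**Falling hazard from the registry table (Protocol VIII.A).** Yearly hazards:
- year 0-1: -ln(0.990) = 0.0101
- years 1-3: ln(0.990/0.972)/2 = 0.0092
- years 3-5: ln(0.972/0.962)/2 = 0.0052
- years 5-8: ln(0.962/0.950)/3 = 0.0042, assumed to continue to year 10

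The cumulative hazard H(10) is 0.0597, so S(10) = 0.942. Scaling by -ln(0.931)/0.0597 = 0.0715/0.0597 = 1.198 sets S(10) = 0.931. Then S(5) = 0.9546, S(7) = 0.9451, and the hazard after year 5 is 0.00501.

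**Error formula.** Assume one knee per subject, a fraction p all lost at year 5, and full follow-up of the rest. With d = H(T) - H(5),

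KM error = p × S(5) × [exp(-d) - exp(-r d)].

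Here d = 5 × 0.00501 = 0.0251 at 10 years and 2 × 0.00501 = 0.0100 at 7 years. Example (T = 10, p = 0.30, r = 3): 0.30 × 0.9546 × (0.9752 - 0.9276) = 0.0137, or +1.4 points.

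| Case (percentage points) | r = 0.5 | r = 2 | r = 3 | r = 5 |
|---|---|---|---|---|
| 10 years, 30% lost | -0.35 | +0.7 | +1.4 | +2.7 |
| 10 years, 10% lost | -0.12 | +0.2 | +0.5 | +0.9 |
| 7 years, 30% lost | -0.14 | +0.3 | +0.6 | +1.1 |
| 7 years, 10% lost | -0.05 | +0.1 | +0.2 | +0.4 |
| 10 years, 30% lost, constant hazard 0.00715 | -0.50 | +1.0 | +1.9 | +3.7 |

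One knee in 138 is 0.72 points, so the first row runs from about -0.5 of a knee to +3.7 knees.

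**Comparison with the CI.** Greenwood variance is S(T)² × {[1/S(5) - 1]/138 + [1/S(T) - 1/S(5)]/[138(1 - p)]}. At 10 years with p = 0.30: 0.931² × (0.000344 + 0.000275), so SE = 0.0232 and the half-width is 1.96 × 0.0232 = 4.5 points. At 7 years it is about 3.9 points (3.8 with 10% lost). For the constant-hazard row it is 4.7. Every error in the table is smaller than its half-width. Censoring at database lock would widen the CI.

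**How few events there are.** Under the falling hazard with 30% lost, expected revisions over a full ten years are 138 × (1 - 0.9546) + 96.6 × (0.9546 - 0.931) = 8.5. Over 1,127 modelled knee-years the pooled hazard is 0.00758, or 1.5 times the 0.00501 that applies after year 5.

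**The case against.** The strongest reply is that the protocol sentence describes handling. It follows the rule that revision is failure and precedes the promise of a KM estimate with a CI. On that reading the SAP does what was promised and 7.15 has nothing to report. The reading is plausible, but it does not rescue the wording: revision as failure is already covered by the preceding sentence, and censoring everything else assesses nothing.

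A second reply is that loss is well controlled. This largely stands. The final evaluation, the exit statuses, telephone contact, tracing and the duty to record revisions mean that a revision at or before exit should be captured. What stays unobserved is mainly revision after exit. These provisions reduce or display the loss but do not bound its effect.

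A third reply is that an illustration can be made to lean high, and this stands too. A multiplier below 1 makes KM too low. The 30% is an allowance for year 10, so applying it by year 5 is pessimistic for a 7-year estimate, and it may also have to absorb deaths. With so few events, any sensitivity range is set mainly by the chosen multipliers.

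Three stronger inferences are tempting, and the documents do not support them:
- That KM overstates survivorship. Nothing shows that loss is informative, or in which direction.
- That SAP 7.10 departs from the protocol by censoring withdrawals. Protocol VI.H provides for exactly that.
- That the error could use up the 7-point margin. In the constant-hazard model above this needs something like a tenfold hazard after loss (93.1 - 85.4 = 7.7 points), and the margin is no longer tested.

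**Conclusion.** The point holds in a limited form. The protocol attributes to KM an assessment that KM cannot make, and the SAP neither provides a substitute nor records the absence. The consequence is confined to how the descriptive estimate and its CI are read.

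Direction and size are unknown. Under the falling-hazard assumptions and multipliers of 0.5 to 5, the error runs from about -0.35 to +2.7 points at 10 years with 30% lost, and from about -0.05 to +0.4 at 7 years with 10% lost. These figures rest on an assumed 93.1% survival, loss concentrated at year 5, full follow-up of retained knees and an extrapolated registry hazard. Priority is minor to moderate.

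**What to change.** In SAP 7.15, or by protocol amendment, state that KM assumes non-informative censoring and does not assess it.

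Add to SAP 7.10:

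1. A table comparing lost or withdrawn knees with retained knees on baseline and last KSS and KOOS, with the reason for exit.
2. One descriptive sensitivity analysis for knees withdrawn or lost to follow-up, leaving out deaths and knees censored at database lock. Report it only at time points that meet a pre-stated minimum number at risk. Either apply multipliers on both sides of 1 (for example 0.5, 1, 2, 3 and 5) to a pooled revision hazard, or give a tipping-point count: how many lost knees would have to have been revised to bring survival down to a stated value. Label the result as driven by the assumed factors because events are few. If a pooled hazard is used, note that it probably overstates late revisions (about 1.5-fold with the registry shape).

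The cost is a few extra tables from data already collected and one corrected statement. Study conduct does not change. The reported range may look less favourable than the single estimate.
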